5.8 Brief In-Person Clinic or Curbside Visits

A brief in-person visit will be scheduled following each of the telehealth visits. Depending on the circumstances, participants may have a brief in-person clinic or a curbside visit. If clinic visits are not optimal (due to COVID-19 prevalence/restrictions, use of public transportation or if a participant is not interested in being seen in the clinic) curbside contact will be arranged. The visits should be scheduled to occur as soon as possible after the telehealth visit. If the visit cannot be scheduled within 24 hours, a partial telehealth visit will occur to update the record. For the brief clinic or curbside pick-up, participants will be required to have a mask of either their own, sent by staff or provided one and told to wear it during the visit. Staff will wear PPE as required (optional if vaccinated. Any sample collection supplies, containers and other handouts will be provided at this time.

During the brief clinic or curbside visit, subjects will drop off the appropriate biosamples, cigarette butts and collect the week's supply of study cigarettes and return empty packs. If there have been device issues with the vitals or CO monitors, they can troubleshoot at this visit.

Biosamples to be returned at this visit:

- 1) First morning void urine collection (Weeks 92, 00, 3, 6, Early Terminating (ET) if applicable)
- 2) Saliva sample obtained for nicotine metabolite ratio-NMR (Week 92)
- 3) Saliva sample for TNEs (Weeks 92, 00, 3, 6, ET if applicable).
- 4) Blood spot (Weeks 00, 6); this collection is optional.
- 5) Hair sample (Week 6); this collection is optional.
- 6) Cigarette butt collection (Weeks 00, 3, 6)

Procedures to be conducted at this visit:

- 1) Oral cells will be collected during the telehealth, in-person curbside or clinic visit. Subjects will be instructed to brush teeth prior to arrival at the visit.
- 2) Inhalation measures (Weeks 00 and 6) will be conducted on a subset of subjects.

5.9 Follow-up

Procedures for Follow-up Telehealth Visit Week 10

Follow-up will occur 4 weeks after the end of the experimental period. Tobacco use status (amount and type of tobacco product use) will be determined. Quitting smoking or staying quit will continue to be strongly encouraged. The following procedures will only involve checking records of product use, vital signs and questionnaires. There is no in-person visit at Week 10.

A. Physiological Measures:

- 1) Vital signs (blood pressure, heart rate) will be obtained while conducting the telehealth visit.
- 2) Carbon monoxide will be obtained while conducting the telehealth visit.

B. Surveys – link sent to participant to complete REDCap based survey (optional – RA enter direct into REDCap):

Subjective Outcome Measures:

- 1) Respiratory Symptoms and Global Health Questionnaire
- 2) Nicotine Dependence Questionnaire

C. Interviews - Research Assistant interviews participant and enters directly into REDCap:

- 1) COVID-19 Assessment
- 2) Health Changes and Menstrual Cycle Questionnaire
- 3) Adverse Events (close out any open events)
- 4) Concomitant Medications
- 5) Tobacco Use 7 Day Followback Form
- 6) Smoking Cessation Counseling
- 7) End of Visit Evaluation

5.10 Early Termination

Procedures for Early Termination Telehealth Visits

If a subject decides to withdraw from the study prior to completion or if they are withdrawn by the Project Leader due to safety concerns, they will be scheduled for an early termination visit. If the participant is contacted within the window of a regularly scheduled visit, all measures for that visit will be collected. If the early termination visit occurs at Weeks 1, 2, 4 or 5, additional safety measures will be obtained since these measures are not scheduled at those visits. If the subject is seen outside the regularly scheduled visit window, safety measures will be obtained.

A. Physiological Measures:

- 1) Vital signs (blood pressure & heart rate) will be obtained while conducting the telehealth visit.
- 2) Carbon monoxide level will be obtained while conducting the telehealth visit.
- 3) Biomarker collection (first void or spot urine and saliva) collected prior to or at the telehealth visit and then dropped off at the brief clinic or curbside visit.

B. Surveys – *link sent to participant to complete REDCap based survey:*

The following additional assessments will be completed at early termination via REDCap, if not part of the usual measures scheduled for the regularly scheduled visit:

Subjective Outcome Measures:

- 1) Respiratory Symptoms and Global Health Questionnaire
- 2) Perceived Health Risk
- 3) Modified Cigarette Evaluation Scale – Study cigarette
- 4) Cigarette Purchase Task – Study Cigarette
- 5) Nicotine Dependence Questionnaire
- 6) Duke Sensory Questionnaire - Study Cigarette
- 7) Tobacco Policy Support Questionnaire
- 8) End of Study and Feasibility Questionnaire

C. Interviews - Research Assistant interviews participant and enters directly into REDCap:

- 1) COVID-19 Assessment
- 2) Health Changes and Menstrual Cycle Questionnaire
- 3) Adverse Event
- 4) Concomitant Medications
- 5) Daily ITR Review (follow-up on missing and unusual reports)
- 6) Timeline Follow-back Questionnaire
- 7) Intention to Quit
- 8) Product Accountability Log
- 9) Smoking Cessation Counseling
- 10) End of Visit Evaluation

5.11 Study Completion:

Any adverse events that remain open from the last study session will be discussed and closed. Once a participant has completed all study procedures and all open events have been closed or designated as ongoing at end of trial, the Site Leader will review the participant's binder and sign a form indicating study completion for that participant. If any of the measures raise concern, the Site Leader will determine if the subject should be followed further.

5.12 Product and Procedures Compliance Review Sessions

At each visit, subjects will be counseled about use of only cigarettes obtained through the study. Participants will be asked about any concerns or obstacles associated with use of the study cigarettes. The importance of honest reporting will be stressed. Participants will be told that it is crucial for them to report any use of products obtained from outside the study, even though it is discouraged. If difficulties are encountered, participants will be asked why they think they are experiencing difficulties (e.g., taste, withdrawal symptoms) and to problem-solve how to deal with these difficulties in order to meet the protocol requirements.

Additionally, participants will be counseled about their Daily ITR text completion, telehealth visit attendance and product accountability. These review sessions should be about 5-10 minutes in length.

5.13 Quit Attempts During the Study Protocol:

At each session, we will ask the participant if he/she is currently abstaining from smoking and/or has the intention of quitting or planning to quit smoking prior to his/her next scheduled visit. If the answer is yes, they will be provided with information on local quit lines to assist them in their quit attempt and a cessation manual provided. If the subject chooses to quit during the study, they will be encouraged to do so and will be offered their choice of 1 box of nicotine replacement products (gum, lozenge or patch) to aid in their quit attempt.

If Currently Abstinent from Smoking:

- Encourage continued abstinence from smoking.
- Provide the cessation manual and local smoking cessation resources.
- Follow visit schedule and procedures.

If a Participant is Planning to Quit Smoking, But Has Not Initiated the Quit Attempt

- Ask if a target quit date has been chosen and document the target quit date.
- Provide the participant with the cessation manual and local smoking cessation resources.
- Recommend that on the target quit date he/she puts any tobacco products "away" so as to avoid unwanted cues to smoke

At the end of the 6-week experimental period, all subjects will be strongly encouraged to stop smoking and if possible, using all tobacco products, and set a quit date. A treatment manual for cessation will be provided and subjects will be encouraged to call the state telephone quit

line. A box of nicotine replacement (e.g., gum, lozenge or patch) will be provided to those who have a quit date or have quit smoking.

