4.2 Inclusion/Exclusion Criteria

Inclusion Criteria

- a) Male or females at least 21 years of age.
- b) Self-report of daily smoking of at least 5+ cigarettes and no more than 35 cigarettes for ≥ 3 months.
- c) Biochemically confirmed regular smoking status (CO ≥ 8 ppm; if CO < 8 ppm, then nicotine level indicating regular smoking).
- d) Smoking a current brand (or if smoking roll-your-own cigarettes, indicates a preferred manufactured brand) of 16-36% ventilation. This range of ventilation was chosen based on our pilot data (unpublished). A list will be provided with eligible brands that corresponds to the predominant type of cigarettes currently used by smokers, i.e., previously marked as "lights" and approximates the assigned ventilated study cigarettes.
- e) Has regular access to a smartphone or tablet for use with CO device and smartphone, tablet or computer with functioning camera and internet access for telehealth visits and surveys.

Exclusion Criteria

- a) Unstable health conditions (any significant serious, unstable medical condition including, but not limited to cardiovascular disease, liver or kidney disease, COPD, bronchitis within the past 3 months, seizure disorder and cancer (cancer-free \leq 5 years except some skin cancers can be within 5 years), or as determined by the licensed medical professional at each site, a COVID-19 positive test or COVID-19 symptoms in the last 30 days).
- b) Unstable mental health (to be determined by medical history, Patient Health Questionnaire (Prime-MD) after review by the licensed medical professional at each site).
- c) Excessive drinking or problems with drinking or drugs-including marijuana (assessed by PI or licensed medical professional).
- d) Use of other tobacco or nicotine products more than 9 days out of the last 30 days.
- e) Currently pregnant, breastfeeding or intending to become pregnant for the duration of the study or unwilling to agree to use adequate protection to avoid pregnancy.
- f) Taking exclusionary medications, unstable dosing of medications, or unstable control of symptoms for ongoing medical conditions (medications or conditions that would impact biomarkers or patient safety to be determined by the licensed medical professional at each site).
- g) Vital signs outside of the following range:
 - i. Systolic BP greater than or equal to 160
 - ii. Diastolic BP greater than or equal to 100

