5.4 Orientation and Screening Phase – Visit 93 and 93a

Cigarette smokers will be screened for eligibility with a brief telephone screener. Eligibility criteria will be aimed towards being inclusionary to ensure generalizability of results to a broader population of smokers. If subjects meet the initial telephone screening eligibility criteria for the study, they will be asked to participate in a more thorough screening via a virtual remote visit using telehealth technology.

Orientation: The purpose of the orientation is to inform the subjects about the study protocol. The Researcher will review the study via telehealth technology with a PowerPoint detailing the study purpose, procedures and risks. The subject is provided a copy of the consent form and HIPPA for review. After the subject has been able to ask questions and receive answers and show comprehension, the consent form and HIPPA will be electronically signed or paper copies mailed back to the Researcher. Signed copies will be provided to the subject at their first brief clinic or curbside visit.

Screening: After obtaining informed consent, basic information and screening questionnaires will be completed to further screen for eligibility.

93. Screening Procedures (see Table of Procedures page 45):

A. *Physiological Measures:*

- 1) Measures will be taken during the brief in-person visit 93a (see below).

B. *Surveys – link sent to participant to complete REDCap based survey:*

Screening forms

- 1) Demographics (including items needed for Masonic Cancer Center registration).

- 2) Brief Medical History Questionnaire to assess current diagnoses, symptoms and past health problems including psychiatric and substance abuse and medication use.
 - a. Concomitant Medication: Current use and use within the prior 30 days.
 - b. Date of last menstrual period and length of cycle will be acquired to assess pregnancy status.
- 3) Patient Health Questionnaire (PHQ/Prime-MD) will be used to assess current symptoms of depression and anxiety. BDI-II and or GAD7 will be administered for clinician to review if positive for depression or anxiety.
- 4) Contemplation Ladder to assess readiness of smoking cessation.
- 5) NIAAA Alcohol Use Questionnaire (12 month version)
- 6) Nicotine Dependence Questionnaire
- 7) Drug Use Questionnaire (1 month version)

C. *Interviews - Research Assistant interviews participant and enters directly into REDCap (except Identification Form):*

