- 2) Carbon monoxide level will be obtained while conducting the telehealth visit.
- 3) Biological sample collection for analysis of nicotine and carcinogen metabolites will be collected prior to (first void urine sample) or at the telehealth visit (saliva and possibly blood spots) and then dropped off at the brief clinic or curbside visit. Oral cells will be collected during the telehealth, in-person curbside or clinic visit. Subjects will be instructed to brush teeth prior to the collection.
- 4) Review Cigarette Butt Collection: The 24-hour collection of cigarette butts prior to this visit will be reviewed and dropped off at brief clinic or curbside visit. These spent filters will be analyzed for cigarette butt staining to inform intensity of smoking behavior.

B. Surveys – link sent to participant to complete REDCap based survey:

Biomarker Modifier Questionnaires:

- 1) Environmental Tobacco Smoke Questionnaire

Subjective Outcome Measures:

- 1) Minnesota Nicotine Withdrawal Scale(MWSC)
- 2) Questionnaire of Smoking Urges-Brief Scale – Study Cigarette (QSU)
- 3) Respiratory Symptoms and Global Health Questionnaire
- 4) Modified Cigarette Evaluation Scale – Study Cigarette
- 5) Perceived Health Risk
- 6) Cigarette Purchase Task – Study Cigarette
- 7) Nicotine Dependence Questionnaire
- 8) Duke Sensory Questionnaire – Study Cigarette
- 9) BDI-II and or GAD7 will be administered for clinician to review if monitored for depression or anxiety.

C. Interviews - Research Assistant interviews participant and enters directly into REDCap:

- 1) COVID-19 Assessment
- 2) Health Changes and Menstrual Cycle Questionnaire
- 3) Adverse Events
- 4) Concomitant Medications
- 5) Daily ITR Review (follow-up on missing and unusual reports)
- 6) Timeline Follow-back Questionnaire (since last visit)

- 7) Randomization to either ventilated or unventilated cigarettes - Read appropriate script
- 8) Intention to Quit
- 9) Product Accountability Log
- 10) Compliance Review
- 11) End of Visit Evaluation

Dispensing Study Product:

At the brief clinic or curbside visit, the participant will be provided their randomized study cigarettes (ventilated or unventilated). The subject will continue to be allocated 150% of their baseline cigarettes per day and receive a \$2 credit per pack for each unused pack of cigarettes that are returned in order to disincentivize wasteful use of cigarettes (sharing with friends, hoarding cigarettes; max credit up to \$30).

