To determine the sample size for a test of non-inferiority for unventilated filter cigarettes compared to ventilated filter cigarettes (control group), we used pilot data from our original ventilated/unventilated study 1 ([name], personal communication). For the purposes of sample size considerations, we will focus on total NNAL as one of the primary outcomes. Seventy subjects had a baseline NNAL value while smoking their usual brand and 19 and 16 subjects had an end of study NNAL value for the ventilated and unventilated groups, respectively. The endpoint of interest is the change in NNAL from baseline. To normalize the distribution of NNAL, the calculations were performed in the log scale. The non-inferiority margin (NIM) was set at a 15% change between groups. This criterion was chosen because it is close to, but not greater than the upper limit of the 95% confidence interval (CI) for the geometric mean of the change in NNAL. Therefore, 73 subjects per group will achieve 80% power to detect non-inferiority for the mean change in NNAL using a one-sided, two sample t-test with a significance level of 0.05. Furthermore, with these sample sizes, a one-sided, two-sample t-test for the mean difference in cigarettes per day (CPD) from baseline will have 90% power to determine non-inferiority with a significance level of 0.05 if the NIM is 2 cigarettes. A mean difference between ventilation groups of less than 2 cigarettes is considered to be in the range of equivalence. To accommodate a 10% loss-to-follow-up rate, we plan to enroll 81 subjects per group for a total of 162.

Study Populations

Intent-to-treat

The first analysis of all primary and secondary endpoints will adhere to the intent-to-treat principle. Under this principle, all subjects randomized to one of the two study arms will be included in the analysis in the group to which they were randomized regardless of protocol violations and compliance to treatment assignment.

Per-Protocol

A second per-protocol analysis will include only participants who complete the 6 week visit without protocol violations or non-compliance.

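### Smoking status is an eligibility check only at visit 93a, so a participant who becomes abstinent in Phase 1 or 2 is still randomised at visit 00 and enters both non-inferiority tests

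*Combined protocol and SAP*

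**What the plan says.** **Entry.** Section 4.2 requires "Self-report of daily smoking of at least 5+ cigarettes and no more than 35 cigarettes for ≥ 3 months", with biochemical confirmation by CO of at least 8 ppm or, below that, a nicotine test. Section 5.4 and footnote 1 of the procedure table place this eligibility check at visit 93a. CO is measured again at visits 92, 91 and 00, but no threshold or eligibility decision is attached to those readings.

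**Between entry and allocation.** Section 5.13 has staff ask at each session about current abstinence and plans to quit. If the participant is currently abstinent, staff encourage this, give cessation resources and "Follow visit schedule and procedures". Neither the exclusions in 4.2 nor the withdrawal criteria in 9.2 name abstinence.

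**Visit 00.** The interview list in section 5.6 includes "Randomization to either ventilated or unventilated cigarettes - Read appropriate script". The dispensing text that follows gives randomised cigarettes at 150% of baseline consumption, with no exception for someone who is not smoking.

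**Analysis.** Under section 10.1, "all subjects randomized to one of the two study arms will be included in the analysis in the group to which they were randomized". The per-protocol set removes protocol violations and non-compliance. Quitting, which the protocol encourages, is not named as either. The missing-data text in 10.2 does not mention it.

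**The concern.** The trial asks whether smoking an unventilated cigarette raises exposure or consumption by more than a margin compared with a ventilated one. Someone who has stopped before allocation is not exposed to either product and cannot inform that comparison. The protocol's own justification of the entry criterion is stability of smoking, yet nothing re-establishes that stability at the point where it matters, after three weeks in which participants are asked weekly about quitting and supported if they do.

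Once randomised, such a person cannot be removed without breaking intent-to-treat, and the per-protocol definition does not clearly remove them either. The only clean place to act is before allocation. At stake are precision and the number of informative participants in a sample size that allows for 10% loss to follow-up and nothing else.

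Section 5.13 (support continued abstinence, carry on with procedures) and the visit 00 text (randomise and dispense) also pull against each other for the same participant and must be reconciled.

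**Working it through.** **1. Following the text for an abstinent participant.** Eligible at 93a; Phase 1 lasts about 1 week and Phase 2 lasts 2 weeks, so allocation comes about 3 weeks later. If the person stops in that interval, 5.13 keeps them on schedule, 4.2 and 9.2 do not remove them, 5.6 randomises and dispenses, and 10.1 analyses them. No step interrupts the sequence.

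**2. What their data look like.** The CPD endpoint in 10.2 is the last 7 days before Week 6 against the Phase 2 mean. Take an assumed 15 cigarettes per day when smoking (4.2 allows 5 to 35):

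| Pattern | Phase 2 mean | Week 6 | Change |
|---|---|---|---|
| Abstinent throughout Phase 2 and at Week 6 | 0 | 0 | 0 |
| Stops halfway through Phase 2, stays abstinent | 7.5 | 0 | -7.5 |
| Abstinent throughout Phase 2, relapses fully | 0 | 15 | +15 |

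So a stable abstainer is uninformative but not extreme on the change scale. Large values come from a quit late in Phase 2 or from relapse after visit 00.

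**3. The plan's own figure.** Section 10.1 states that "73 subjects per group will achieve 80% power to detect non-inferiority for the mean change in NNAL using a one-sided, two sample t-test", at a one-sided level of 0.05. For the margin, "The non-inferiority margin (NIM) was set at a 15% change between groups", taken here as ln(1.15) = 0.1398. The same 73 per group is said to give 90% power for CPD with a margin of 2. No SD is stated, so 73 cannot be reproduced independently; it can only be solved backwards. With a true difference of 0 (also an assumption) and the noncentral t distribution:

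- log NNAL: SD = 0.338 (0.340 by the normal formula 0.1398 / [(1.645 + 0.842) × √(2/73)])
- CPD: SD = 4.11 (4.13 by the normal formula 2 / [(1.645 + 1.282) × √(2/73)])

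On this scale the changes of 7.5 and 15 in step 2 are 7.5/4.11 = 1.8 SD and 15/4.11 = 3.6 SD.

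**4. Variance added by quitters at any time.** If a share f of each arm has a mean shift d, then SD_mix = √(SD² + f(1-f)d²). Both f and d are assumptions. At f = 0.03, f(1-f) = 0.0291:

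| Endpoint | Shift | SD_mix | Power, 73 per group |
|---|---|---|---|
| NNAL | 60% fall, d = ln 0.4 = -0.916 | √(0.1142 + 0.0244) = 0.372 | 73% |
| NNAL | 80% fall, d = ln 0.2 = -1.609 | √(0.1142 + 0.0754) = 0.435 | 61% |
| CPD | fall of 10 | √(16.89 + 2.91) = 4.45 | 85.5% |
| CPD | fall of 15 | √(16.89 + 6.55) = 4.84 | 80% |

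Across other rates, NNAL power is 78-73% at f = 1% and 69-53% at f = 5%.

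**5. What a check at visit 00 could recover.** The shifts in step 4 mostly describe people who smoke through visit 00 and stop later; a check before allocation does not touch them. If one third of the 3% were identifiable at visit 00 (an assumption; the documents give no share), f falls to 2%. NNAL power is then 75-66% instead of 73-61%, a gain of about 2 to 5 points.

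**The case against.** **The power losses belong to a different group.** This stands. The 5.13 bullet concerns people abstinent before allocation, and the modelled losses are driven by later quits. A reader might infer that the gap puts extreme values into both co-primary endpoints. For a stable abstainer the CPD change is near 0, so that holds only for late Phase 2 quits and relapses.

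**No bias follows.** This also stands. Status fixed before randomisation is balanced in expectation. A reader might treat a chance excess of abstainers in one arm as a further harm, but that is sampling variation already counted in the larger SD.

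**The printed order at visit 00 proves nothing.** Randomization is listed as item 7 and Intention to Quit as item 8, from which one might infer that the answer comes after allocation. Section 11 says each visit has a checklist setting the order of administration, and it is not in these documents. CO, the daily-text review and Timeline Follow-back are listed ahead of randomisation, so abstinence would probably be visible. But visibility without a rule changes nothing.

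**Planned quitters should be excluded too.** This stronger reading is tempting because screening includes "Contemplation Ladder to assess readiness of smoking cessation". The documents do not support it. No cut-off is given for the Ladder, the Intent to Quit form in 6.1 looks only as far as the next visit, and 5.4 aims for inclusive criteria. For people planning to quit, 5.13 lists documentation and materials and does not repeat the schedule instruction; the point there is silence, not a directive.

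**Quitters can be identified later.** Self-reported abstinence is to be confirmed by TNE (5.15), which helps sensitivity analyses but does not settle who is randomised.

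**Conclusion.** The gap is real: followed as written, the plan randomises participants known to be abstinent, dispenses cigarettes to them, and carries them into the intent-to-treat tests. The consequence is lost information and some added variance, not systematic bias.

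Its size cannot be taken from the documents, which give no SD, no quit rate and no expected change in quitters. The fall in NNAL power from 80% to 73-61% at an assumed 3% of quitters covers quits at any time. It is a ceiling on what a check at visit 00 could recover; under the one-third assumption the gain is 2 to 5 points. These figures also assume a true difference of zero and that the back-solved SD contains no quitters. The case for change rests less on the power figure than on the low cost of asking that a participant be a smoker when allocated to a cigarette.

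**What to change.** 1. State in 4.2 and 5.6 that current smoking is a condition of randomisation at visit 00. Before allocation, review the CO, daily-text and Timeline Follow-back data already collected at that visit and ask the 5.13 abstinence question. Define in advance what counts as abstinent.
2. Do not randomise a participant who is abstinent at that point. Replace them; since they have not been allocated, intent-to-treat is unaffected.
3. Reconcile 5.13 with the visit 00 randomisation and dispensing text, so that one participant is not subject to both.
4. Keep quits after randomisation in the intent-to-treat analysis, and say how they are classed in the per-protocol set.

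Do not add an exclusion for any plan to quit before Week 6: current forms cannot identify it, and it would narrow the population.

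**Cost:** one eligibility line and a stated order for existing items. A few participants are lost before randomisation and must be replaced.
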